4. AMENDMENTS AND UPDATES

5. MILESTONES

Milestone	Planned date	
Start of data collection	Before the end of the first northern	
	hemisphere influenza season following	
	marketing authorisation.	
End of data collection	An update report will be filed with the	
	EMA each year, providing details of the	
	number of treated patients enrolled and	
	guidance on the likely study end date.	
Final report of study results	Within 6 months after eCRF completion	
	for last subject	

6. RATIONALE AND BACKGROUND

6.1. Background

Pregnant women are recognised as a group at increased risk of severe disease and death secondary to influenza infection mainly based on observations of excess influenza-related mortality in pregnant women during historical and recent pandemics [Harris, 1919; Freeman, 1959, Siston, 2010] and higher rates of influenza-related morbidity requiring hospitalisation during seasonal epidemics [Dodds, 2007; Neuzil, 1998; Mertz, 2013]. For example, in the United States, pregnant women had a 4-fold greater risk of hospitalisation due to A/H1N1 infections compared to the general population in the pandemic of 2009/2010 [Jamieson, 2009]. In addition, influenza and fever may increase the risk of adverse pregnancy outcomes [Meijer, 2015; Siston, 2010; Mosby, 2011; Haberg, 2013]. These effects were confirmed in the United Kingdom where risks of perinatal mortality, as well as preterm birth, were 4-fold greater in mothers infected with A/H1N1 during pregnancy [Pierce, 2011]. Furthermore, a recent systematic review and meta-analysis reported an association between severe A/H1N1 disease and preterm birth and foetal death [Fell, 2017].

In the European Union, oseltamivir, taken orally, zanamivir which is inhaled, peramivir which is a solution to be diluted and used as an infusion and now intravenous zanamivir, are the four approved neuraminidase inhibitors (NAIs). Early treatment of influenza with oseltamivir has been associated with a reduced risk of severe infection and of admission to intensive care units (ICU) for pregnant women [Meijer, 2015; Delgado-Rodriguez, 2012]. Prior to the last influenza pandemic of 2009 there were few data on NAI safety in pregnancy. A recent European study of population-based registers from Denmark, Norway and Sweden and France captured data reflecting increased uptake of NAIs in pregnant women following the 2009 pandemic. Data from prescription registers, capturing NAI exposure during pregnancy, were linked to birth registers capturing information on pregnancy outcomes. Exposure to NAIs during pregnancy was not associated with increased risks of neonatal outcomes including LBW, SGA, preterm birth, stillbirth, neonatal death and neonatal morbidity. First trimester exposure was not associated with an increased risk of congenital malformations [Graner, 2017]. Although 74% of the NAIs exposures during pregnancy were to oseltamivir, data specific for zanamivir (including 321 first trimester zanamivir exposures) were not reported separately. Several additional observational studies of inhaled zanamivir exposure in pregnancy, with sample sizes ranging from 50 to 180 inhaled zanamivir exposures during any trimester of pregnancy, have failed to report a significant increase in adverse pregnancy outcomes [Walker, 2014; Saito, 2013; Dunstan, 2014].

Pre-clinical studies in rats and rabbits have failed to identify increased risks for malformations, maternal toxicity, or embryotoxicity following intravenous (IV) administration of zanamivir at doses up to 90 mg/kg/day. A further embryofoetal development study following subcutaneous administration of zanamivir at doses of up to 80 mg/kg, 3 times daily (240 mg/kg/day), observed an increase in the incidence rates of a variety of minor skeleton alterations and variants in the offspring at systemic exposure greater than approximately 3 times the human exposure at the clinical intravenous dose (600 mg twice daily). In most instances, the individual incidence rate of each skeletal alteration or variant remained within the background rates of the historical occurrence in the strain studied.

No randomised controlled trials have studied the effect of inhaled and IV zanamivir exposure on pregnancy outcomes.

Due to limited treatment options, antiviral drug resistance remains a public health concern, and alternative treatments to oseltamivir are needed in case of widespread resistance. Although orally inhaled zanamivir has been shown to be less prone to drug resistance, there is also an unmet medical need for patients who are unable to take oral or actively inhaled medications; e.g. children, patients who are not awake or strong enough to inhale, patients with underlying lung disease, or patients on mechanical ventilation, for which there are limited treatment options. GlaxoSmithKline (GSK) initiated the clinical development of an intravenous formulation of zanamivir (IV zanamivir) in response to the 2009 influenza A/H1N1 pandemic. A global compassionate use program (CUP) was initiated in May 2009 at the onset of the A/H1N1 influenza pandemic to provide IV zanamivir on a named-patient basis to seriously ill patients with suspected or confirmed influenza for whom approved anti-influenza drugs were not effective or not feasible. IV

zanamivir is administered as a 600mg dose twice daily that is infused over a 30-minute period. The recommended course is for 5 days, but can be extended depending on disease severity and progress

GSK has gained approval under exceptional circumstances for IV zanamivir in the EU. The indication is for the treatment of complicated and potentially life-threatening influenza A or B virus infection in adult and paediatric patients (aged ≥ 6 months) when:

- The patient's influenza virus is known or suspected to be resistant to antiinfluenza medicinal products other than zanamivir, and/or
- Other anti-viral medicinal products for treatment of influenza, including inhaled zanamivir, are not suitable for the individual patient.

Dectova should be used in accordance with official guidance.

Given that pregnant women are a group at high risk of influenza related morbidity and mortality, exposure to IV zanamivir in pregnancy is likely.

6.2. Rationale

This prospective observational study aims to evaluate pregnancy outcomes among women hospitalised with complicated influenza and exposed to IV zanamivir during pregnancy in the European Union, UK, Iceland and Norway.

7. RESEARCH QUESTION AND OBJECTIVE(S)

The objective of the Zanamivir 10 mg/mL solution for infusion pregnancy registry is to evaluate pregnancy outcomes among women exposed to IV zanamivir at any time during pregnancy. Outcomes of interest will include: 1) maternal outcome of maternal death, 2) pregnancy outcomes including spontaneous losses in clinically recognised pregnancies, IABs, stillbirths and live births and 3) birth outcomes including low birth weight, small for gestational age, prematurity, congenital malformations and neonatal death.

This registry is primarily descriptive and designed to detect potential safety signals rather than test hypotheses.

8. RESEARCH METHODS

8.1. Study Design

The IV zanamivir pregnancy registry is a prospective, observational study of pregnant women treated with IV zanamivir at any time during pregnancy. It will be based on exposures during pregnancy reported through the UKOSS and the INOSS as the principal sources for exposure identification and will be strictly observational; the schedule of healthcare visits and encounters and all treatment regimens will be determined by the treating HCP. The registry will collect data that are routinely documented in the patient's medical record as part of usual care.

8.2. Study Population and Setting

Once initiated, pregnant women exposed to IV zanamivir in the European Union, United Kingdom (UK), Iceland and Norway identified through UKOSS and INOSS will be eligible to be enrolled in the pregnancy registry.

UKOSS is a well-established national system to collect information about severe maternal morbidity through more than 700 collaborating clinicians in all 198 hospitals with consultant-led maternity units throughout the UK (see www.npeu.ox.ac.uk/ukoss for further information). All hospitals in the UK with a consultant-led maternity unit collaborate in UKOSS, and thus it is an ideal mechanism to maximise identification of exposures of IV Zanamivir in women hospitalised with influenza across the UK, as well as to collect information on their management and outcomes. This system has been demonstrated to be able to rapidly collect information to inform policy and guidance in a previous pandemic [ANZIC, 2010; Jamieson, 2009]. INOSS is the equivalent population-based network across other European countries. INOSS networks have similar but varying set-ups, which will be used and adapted for this study. The main addition to the existing UKOSS and INOSS structures will be with the addition of an infant follow-up at 3 months and the ability to follow regulatory pharmacovigilance reporting procedures enabled by OXON.

The data collection process for each participant will begin at enrolment (during pregnancy) with follow-up to occur at pregnancy outcome (delivery or early termination) and out to 3 months post-delivery for live births to capture maternal deaths, neonatal deaths and to increase ascertainment of congenital anomalies.

The study population will include pregnant women in the European Union, UK, Iceland and Norway hospitalised with complicated influenza who received at least one dose of IV zanamivir at any time during pregnancy and are identified through the UKOSS and INOSS networks. IV zanamivir should be used during pregnancy only if clearly needed, and exposure during pregnancy may be expected because pregnant women represent a group at risk of hospitalisation with complicated influenza for which an IV formulation may be needed.

The minimum criteria required for enrolment into the registry will include:

- Sufficient evidence to confirm that exposure to IV zanamivir occurred at any time during pregnancy based on information from the reporter.
- Sufficient information to determine whether the pregnancy is prospectively or retrospectively recorded (i.e., whether the outcome of pregnancy was known at the time of first contact with the registry).
- Date of enrolment into the registry.
- Treating hospital contact information to allow for follow-up.
- Women aged >18 years at time of enrolment.

If it cannot be ascertained to which anti-influenza medication the woman was exposed, an unknown exposure cohort will be established and analysed separately. Pregnancy exposures ascertained prospectively (before the outcome of pregnancy) will initially be analysed separately from those ascertained retrospectively.

Patients will be identified through UKOSS and INOSS networks and data collection will be coordinated through study staff and the study contract research organization (CRO) (OXON).

It will also be possible to supplement study data using de-identified data provided by HCPs under the waiver of informed consent provision. This could include exposures and outcomes identified through anonymised healthcare electronic medical record data sources.

All study information materials will be in accordance with the approved Prescribing Information Documentation in the EU.

Reference Groups

Given the inherent difficulties in identifying a comparison group within a pregnancy registry [Covington, 2009], several different methods may be used to review the data for safety signals. As described below, background prevalence estimates from external surveillance sources and estimates from published literature will be the primary comparators. To the extent possible, comparator prevalence estimates will be age-adjusted to reflect the age distribution of the pregnancy registry population and will also consider disease severity.

An untreated disease comparator group is unlikely to be feasible to recruit within the registry as national and international guidelines are to treat pregnant women with influenza antivirals due to an increased risk of morbidity associated with influenza. As other NAIs approved in the European Union are not specifically indicated for the treatment of complicated influenza, appropriate comparators by disease severity are also likely to be difficult to identify outside of surveillance programs and the literature. Comparisons between inhaled and IV zanamivir exposures will also be inappropriate due to difference in the underlying severity of disease associated with mode of treatment administration.

As treatment options may change over time, potential comparators will be assessed on a regular basis and if possible, a concurrent comparator group of IV zanamivir unexposed pregnant women with complicated influenza will also be recruited into the registry.

Background Prevalence Estimates of Pregnancy Outcomes

Background prevalence estimates of pregnancy outcomes in the general population, such as premature birth and LBW, are readily available from national vital statistics or publications in the scientific literature [Office for National Statistics, 2015]. Rates for a range of countries participating in the registry will be reviewed so that variation in background rates can be considered.

Background Prevalence Estimates of Major Congenital Malformations (MCMs)

Published prevalence estimates of MCMs are available from the European Registry of Congenital Malformation and Twin Registries (EUROCAT) which is an ongoing population-based birth defects surveillance program across Europe [EUROCAT, 2017]. EUROCAT is a European network of population-based registries covering 29% of the European population. It started in 1979 and covers 1.5 million births per year in Europe. Its primary objectives are to provide essential epidemiological information on congenital

malformations and to act as an information and resource centre to individuals and public health professionals.

As EUROCAT is primarily a passive surveillance system, background prevalence estimates from active surveillance approaches will also be considered. The Centre for Disease Control and Prevention's (CDC) Metropolitan Atlanta Congenital Defects Program (MACDP) actively searches for congenital malformations among the 50,000 annual births to residents of metropolitan Atlanta's 5 counties and abstracts medical records at all Atlanta obstetric hospitals, paediatric referral hospitals, genetics laboratories, and vital records [Correa-Villasenor, 2003]. MACDP data have been used as the comparator cohort in examinations of congenital malformations for other pregnancy registries despite differences in geographic focus (for example with other GlaxoSmithKline products including acyclovir, sumatriptan, lamotrigine, and zidovudine) [Honein, 1999]. The most recent CDC MACDP 5-year major malformation prevalence was 2.78% (6,945 cases with birth defects/249,999 live births) from 1999 to 2003.

In the absence of appropriate influenza disease-based comparators these will form the primary population-based comparator groups.

Background Prevalence Estimates from Literature or Other Studies

The registry will identify other appropriate comparison groups through research of the literature and other sources, such as other pregnancy registries or observational studies. Particular attention will be paid to identify appropriate disease-based comparators in the literature, specifically pregnant women with influenza.

Concurrent comparator of untreated influenza pregnant women

Influenza itself is associated with adverse pregnancy outcomes and increased maternal influenza related mortality and morbidity. General population comparator groups will therefore not represent the same baseline risk of adverse pregnancy outcomes as women with influenza exposed to IV zanamivir. As treatment options may change over time, potential comparators will be assessed on a regular basis to assess if it will be feasible to enrol a disease comparator group that is unexposed to treatment or unexposed to IV zanamivir with similar underlying disease severity (complicated influenza).

8.3. Variables

Key clinical data that will be collected for this study are described below.

8.3.1. Exposure definitions

This pregnancy registry is strictly observational and confirmed exposure to IV zanamivir at any time during pregnancy is a condition of enrolment. The exposure of interest is exposure to at least one dose of IV zanamivir during pregnancy. If the anti-influenza medication to which the woman was exposed cannot be ascertained, an unknown exposure cohort will be established and analysed separately.

Data to be collected include the date of medication exposure and dose.

8.3.2. Outcome definitions

There are three groups of outcomes of interest:

Maternal outcomes

• Maternal death during pregnancy and up to 42 days after delivery.

Pregnancy outcomes

- Live birth defined as an infant born alive.
- Spontaneous abortion (SAB) in clinically recognized pregnancies defined as foetal death or expulsion of products of conception prior to 20 weeks' gestation, or if gestational age is unknown, weighing less than 500g.
- Stillbirths defined as a foetal death occurring at 20 weeks' gestation or greater, or if gestational age is unknown, a foetus weighing 500 g or more.
- IAB defined as voluntary interruption of pregnancy, including pregnancy termination that occurs electively, to preserve maternal health, or due to foetal abnormalities.

Birth outcomes

- Prematurity defined as an infant born at gestational age <37 weeks.
- SGA defined as an infant born with a birth weight less than the 10th centile for the corresponding gestational age.
- LBW defined as an infant whose birth weight is <2500 g.
- Neonatal death defined as death of the infant within 28 days of birth.
- Major congenital malformation (MCM) defined according to EUROCAT criteria
- EUROCAT includes all major structural malformations and chromosomal malformations. Minor anomalies are excluded (as defined in Section 3.2 of the coding guide) and cases with more than one malformation type are only counted once for the calculation of overall malformation prevalence.

Maternal and infant follow up is proposed to 3 months after birth. Longer term follow-up is not proposed as there are no pre-clinical or clinical data to suggest a signal for developmental delay. Hence, it is impossible to determine an appropriate longer term follow up period which differs substantially according to the type of developmental adverse outcome of interest. As the majority of major malformations are detected at birth, a three month follow up period is deemed adequate to maximize capture of major malformations.

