This pregnancy registry will be a multi-centre, prospective observational cohort study using the United Kingdom Obstetric Surveillance System (UKOSS) and International Obstetric Surveillance System (INOSS) as the principal sources to identify IV zanamivir exposed pregnancies. The registry will collect data directly from healthcare providers (HCPs) based on information that is routinely documented in the participant's medical record as part of usual clinical care. Data will be collected at enrolment as close as possible to the time of exposure to IV zanamivir in pregnancy and at pregnancy outcome (delivery or early termination) with follow up out to three months after delivery to increase birth outcome ascertainment in the infant.

Population

Pregnant women with complicated influenza who have been exposed to at least one dose of IV zanamivir during pregnancy will be eligible to participate in the registry. Minimum criteria for enrolment will be the following:

- Sufficient evidence to confirm exposure to IV zanamivir during pregnancy based on information from the reporter.
- Sufficient information to determine whether the pregnancy is prospectively or retrospectively recorded (i.e., whether the outcome of pregnancy was known at the time of enrolment).
- Date of enrolment into the pregnancy registry.
- Treating hospital contact information to allow for follow-up.
- Women aged >18 years at time of enrolment.

Identification largely via the UKOSS and INOSS systems is proposed, followed by enrolment study staff. De-identified data provided by HCPs under the waiver of informed consent provision will also be collected where allowed under local country laws.

Variables

The exposure of interest will be IV zanamivir during pregnancy.

Outcomes of interest will include: 1) maternal death, 2) pregnancy outcomes including spontaneous losses in clinically recognised pregnancies, induced abortions, stillbirths and live births and 3) birth outcomes including low birth weight, small for gestational age, prematurity, congenital malformations and neonatal death.

Covariates of interest will include: maternal age and ethnicity; prenatal data including estimated date of delivery (EDD); prenatal tests, obstetric history, current pregnancy complications, clinical details of influenza episode, other co-morbidities, concomitant medication exposure and smoking use during pregnancy as well as infant gender and multiple gestations.

Data Sources

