8.6.2. Resourcing needs

The implementation, management and closure of this study will be outsourced to a CRO, OXON Epidemiology. The study will be overseen at GSK by a PhD level Epidemiologist and a Study Delivery Lead.

Biostatistical and methodological issues will be addressed by a senior level statistician with expertise in observational data either from the CRO, or similar, or from within GSK.

8.6.2.1.	Timings of Assessment during follow-up
----------	--

Information requested	Registration provided by HCP	Pregnancy outcome provided by research staff up to 3 months post- delivery	Targeted follow up to collect information not previously obtained, provided by research staff
Maternal contact	Х	Xa	
information, alternate			
contact information, HCP			
contact information			
Maternal characteristics	Х		
(age,ethnicity, etc.)			
Maternal prenatal	Х	Xa	
information (LMP, EDD,			
CEDD, prenatal test			
results and timing)			
Obstetrical history	Х		Xp
Family history of MCMs	X		Xb

Information requested	Registration provided by HCP	Pregnancy outcome provided by research staff up to 3 months post- delivery	Targeted follow up to collect information not previously obtained, provided by research staff
IV zanamivir exposure information	X	Xa	
Influenza episode clinical details	X	Xa	
Pregnancy complications	Х	Xa	
Other Concurrent conditions and concomitant medications, tobacco use during pregnancy	X	Xa	
Pregnancy status		Х	
Outcome information (maternal death, live birth, still birth, SAB, gestational age, birth weight)		X	Xp
MCM noted and description		X	Xp

Abbreviations: CEDD = corrected estimated date of deliver; EDD = estimated date of delivery; HCP =health care provider; LMP = last menstrual period; MCM(s) = major congenital malformation(s); Ob =obstetric; SAB = spontaneous abortion.

a Obtain updated information since the previous contact.

b Targeted follow-up is designed to collect addition information (if necessary) to facilitate characterization of the foetal loss, MCMs and/or neonatal death.

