Retrospective reports include subjects for whom the pregnancy outcome has already occurred. Retrospective reports can be biased toward the reporting of more unusual and severe cases and are less likely to be representative of the general population experience than exposures reported prior to knowledge of outcome. Although the exposure can be identified objectives through the UKOSS/INOSS systems, there is still the potential for bias to be introduced if there are delays in the women consenting and between exposure and consent there is additional knowledge of the outcome of the pregnancy. Where possible, the characteristics of prospective and retrospective reports will be compared to assess potential bias. If there is adequate evidence to support lack of bias these prospective and retrospective reports may be combined for analysis, but the initial analysis position will be for retrospective reports with reported MCMs and/or SABs will be reviewed to aid in detection of early signals and listed in registry reports.

Loss to Follow-up

For a prospective report of pregnancy where follow-up information on the pregnancy outcome (live birth, SAB, etc.) is never obtained or is unavailable, the pregnancy will be considered lost to follow-up. Subjects lost prior to pregnancy outcome will be tallied in the registry reports but not included in the statistical analyses.

Duplicate Registry Reports

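### Maternal death is counted to 42 days after delivery, but no maternal follow-up window exists after a spontaneous or induced abortion, and the windows given for stillbirth conflict

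*Protocol*

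**What the plan says.** - **Definition (Section 8.3.2).** The maternal outcome is "Maternal death during pregnancy and up to 42 days after delivery".
- **Follow-up (Section 8.2).** The plan is for "follow-up to occur at pregnancy outcome (delivery or early termination) and out to 3 months post-delivery for live births to capture maternal deaths". This is the only place that names a mechanism for finding maternal deaths after the pregnancy has ended.
- **Abstract, Study Design.** Data are collected "at pregnancy outcome (delivery or early termination) with follow up out to three months after delivery", and the stated purpose of the later follow-up is better ascertainment in the infant.
- **Section 8.3.2, closing paragraph.** "Maternal and infant follow up is proposed to 3 months after birth". There is no restriction to live births here.
- **Assessment schedule (Section 8.6.2.1).** The outcome column is headed "Pregnancy outcome provided by research staff up to 3 months" post-delivery. Maternal death shares a row with live birth, stillbirth and spontaneous abortion.
- **Denominator (Section 8.7.1).** Maternal deaths are divided by the number of exposed pregnancies, whatever their outcome.
- **Loss to follow-up (Section 8.7).** A report is lost when the pregnancy outcome is never obtained: "Subjects lost prior to pregnancy outcome will be tallied in the registry reports but not included in the statistical analyses". Maternal vital status plays no part in this rule.

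**The concern.** A prevalence needs a numerator looked for in everyone who is in the denominator. Here the denominator includes pregnancies that end in spontaneous abortion, induced abortion or stillbirth, while the period in which a maternal death is sought is tied to delivery and, in Section 8.2, to live birth. A woman with a recorded loss and unknown status six weeks later is not lost to follow-up under Section 8.7. She stays in the analysis as a non-death.

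This could matter because the women without a window are plausibly not a random subset. The background section cites an association between severe A/H1N1 disease and foetal death, and the definition of induced abortion in Section 8.3.2 includes terminations done for the mother's health. Maternal death is the first outcome in the objective of a registry built to find safety signals, and the error can only lower the estimate.

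**Working it through.** **1. The plan's own figures.** The only computed figures are the detectable ratios in Table 1 (Section 8.5). They reproduce with an exact one-sample binomial calculation at 1-sided 5% and 80% power. At 100 live births the critical counts are 13 (preterm birth), 12 (low birth weight) and 6 (major malformation), giving ratios of 2.05, 2.07 and 3.90 as stated. Maternal death is not in the table, so this point changes no stated figure.

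**2. The sections side by side.**

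| Pregnancy ends in | 42-day definition (8.3.2) | Follow-up in 8.2 | Follow-up in 8.3.2 (after birth) | Schedule 8.6.2.1 (post-delivery) | In denominator (8.7.1) |
|---|---|---|---|---|---|
| Live birth | applies | 3 months | 3 months | 3 months | yes |
| Stillbirth | can apply | outcome contact only | 3 months can apply | 3 months can apply | yes |
| Induced abortion | not covered | outcome contact only | not covered | no window given | yes |
| Spontaneous abortion | not covered | outcome contact only | not covered | no window given | yes |

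The last two rows follow because Section 8.2 and the Abstract list delivery and early termination as alternatives. For those rows no section supplies a window. For stillbirth the gap comes from Section 8.2 alone, which conflicts with the other two.

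**3. Whether another section closes the gap.** Targeted follow-up is marked for the outcome row in Section 8.6.2.1, but its footnote gives the purpose as characterising foetal loss, malformations and neonatal death, not maternal death. Section 11 collects general maternal adverse events only to 24 hours after treatment ends. It also collects events defined as study endpoints, but these take their definition, and so the 42-day anchor, from Section 8.3.2.

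**4. Size, on assumptions only.** The documents give no loss rate, mortality or timing of deaths. Let

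- f = share of pregnancies ending without a maternal window,
- q = share of maternal deaths in that group that occur after the pregnancy ended,
- k = risk of death in that group relative to the others.

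The share of all maternal deaths falling outside follow-up is k·f·q / (k·f + 1 − f). This is a ceiling, because it treats every such death as unknown at the outcome contact.

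- k = 1: from 0.05 × 0.25 = 1.3% to 0.20 × 0.75 = 15%.
- k = 3: from (3 × 0.05 × 0.25)/(0.15 + 0.95) = 3.4% to (3 × 0.20 × 0.75)/(0.60 + 0.80) = 32%.

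The width of the range shows that the size is not determined.

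**5. What one uncounted death does to the estimate.** With 100 pregnancies, the exact 2-sided 95% limits are 0 to 3.6% for 0/100, 0.03% to 5.4% for 1/100, and 0.2% to 7.0% for 2/100.

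**The case against.** The best defence is that many such deaths would be recorded anyway. Maternal death stands beside spontaneous abortion and stillbirth on the outcome form, so a death known when the form is completed is captured. Influenza details, including hospital and intensive-care stay, are updated at that contact, and a woman who loses a pregnancy during complicated influenza and dies soon afterwards may well die in the same admission. No section says that follow-up stops after a loss. Section 8.7 also expects most exposure to occur after prenatal screening, which makes early losses less common. All of this stands. It limits the claim to deaths that are not systematically captured, but it does not supply a window.

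Three stronger readings are tempting, and the documents do not support them.

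- *All deaths after a stillbirth fall outside the plan.* A stillbirth involves a delivery, so the definition can reach it. The problem there is one conflicting section.
- *A woman who dies with no recorded pregnancy outcome is excluded by rule.* Section 8.7 can be read that way, but Section 8.6.2.1 lists maternal death as outcome information and no text says that a reported death is discarded. This is an ambiguity to clear up.
- *One missed death would reverse the conclusion.* Against an assumed reference of 0.01% to 0.05%, one death in 100 does give an exact 1-sided P of 0.010 to 0.049. That reference is not in the documents. Section 8.2 says that general-population comparators do not share the baseline risk and that comparators will take severity into account. A reversal also needs no counted death among the other women. If 85 others had an assumed mortality of 1% to 5%, the chance of at least one counted death would be 1 − 0.99^85 = 57% to 1 − 0.95^85 = 99%.

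**Conclusion.** The gap is real. For spontaneous and induced abortion, neither the definition nor any follow-up statement covers the 42 days. For stillbirth, Section 8.2 contradicts Sections 8.3.2 and 8.6.2.1. Since the denominator is all exposed pregnancies, deaths after a loss that are not known at the outcome contact are counted as survivals, and maternal-death prevalence is biased downward.

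The size of that bias cannot be obtained from the documents, and the percentages in the working illustrate assumptions only. The conclusion rests on reading delivery as distinct from early termination, as the protocol itself does.

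The registry is descriptive and maternal death does not drive its size, so this should be fixed but does not undermine the design. It cannot be left to the analysis plan, which could not recover vital status that was never collected.

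**What to change.** 1. In Section 8.3.2, define maternal death as death during pregnancy or within 42 days of the end of pregnancy, whatever its outcome.
2. Align the Abstract and Sections 8.2, 8.3.2 and 8.6.2.1 so that maternal vital status at day 42 or later is taken from routine records for every enrolled woman.
3. Report the number of women with known day-42 status beside the prevalence, so that readers can see how complete the numerator is.
4. In the loss-to-follow-up paragraph of Section 8.7, state that a known maternal death is itself an outcome and is analysed even where the pregnancy outcome is not recorded.

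The cost is a change of wording in five places and one extra abstraction item for the minority of women without a live birth. It needs no added visit or test, and Table 1 is unaffected.
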